### **5.3. Per Protocol (PP) Population**

The Per Protocol (PP) population will be a subset of ITT population consisting of those subjects who complete 14 days treatment and had no major protocol deviation affecting the primary efficacy variable. All protocol deviations will be assessed and documented on a case-by-case basis before the database lock, and deviations considered to have a serious impact on the efficacy results will lead to the relevant subject being excluded from the PP population. Before database lock, potential subject exclusions from PP population will be reviewed by the Sponsor and documented in a subject evaluability document.

### **5.4. Pharmacokinetic (PK) Population**

The PK population will include all subjects who receive at least 1 dose of study treatment with sufficient post dose plasma concentration data. This population will be used for PK analysis, summaries will be provided by actual treatment received.

### **5.5. Pharmacodynamic Population**

Not applicable for this study.

### **5.6. Other Analysis Population**

Not applicable for this study.

### **5.7. Protocol Deviations**

All subjects protocol deviations will be summarized with number and percentage by treatment group: Protocol deviations data will be summarized on all randomized subjects.

A listing will be produced containing the following information:

- Date
- Minor or Major deviation
- Category of deviation
- Description of deviation

The listing will be presented for the all randomized subjects.

## **6. General Aspects for Statistical Analysis**

### **6.1. General Methods**

The statistical evaluation will be performed using SAS® software version 9.4 or higher (SAS Institute, Cary, NC). All data will be listed, and summary tables and figures will be provided.

- Summary tables will be organized by treatment group. Descriptive statistics for continuous variables will include number of subjects (n), mean, standard deviation, median, minimum, and maximum, unless otherwise noted. Frequency and percentage will be calculated for categorical variables. Unless stated otherwise, all summary tables will present descriptive statistics and/or frequencies by treatment.
- All data listings will be sorted by treatment and subject number. Data listing will be provided for all randomized subjects with exception of few listings which will be provided for all enrolled subjects.
- Unscheduled assessments will not be included in summary tables unless specified otherwise but will be included in the subject listings.

### **6.2. Key Definitions**

#### **6.2.1. Baseline**

In general, the last non-missing valid observation before first dose of study drug will serve as the baseline measurement.

#### **6.2.2. Body Mass Index**

The BMI of a subject will be calculated in kg/m^2 as BMI = body weight [kg] / (height [m]).

#### **6.2.3. Change from Baseline**

Change = Post-baseline value – Value at baseline.

Relative change = [(Post-baseline value – Value at baseline) / Value at baseline] x100.

#### **6.2.4. Treatment Accountability and Compliance**

The pharmacist or other designated individual will maintain records of study treatment delivered to the study site, the inventory at the study site, the distribution to and use by each subject and the return of any required materials to the Sponsor. Study sites will be responsible for disposal of study treatment. Records should include dates, quantities, batch/serial numbers, expiration dates, in-clinic temperature log, and unique code numbers assigned to the product and study subjects.

At each visit after initiation of treatment, study site personnel will record compliance of the subject with the subject's assigned regimen. Subjects will be instructed to bring their sleep diaries and unused/partially used/empty bottles back for inspection at each study visit. Subjects are to be reminded of the importance of compliance with their assigned regimen, with an emphasis on taking their study drug on schedule and maintaining the prescribed interval between doses.

Subjects with missing sleep diaries or with missing entries in sleep diaries for dosing will be considered as treated if number of tablets returned at post baseline visit are less than the number of tablets dispensed at baseline visit.

Investigators will maintain records that adequately document that the subjects were provided with the correct study treatment kits and reconcile the products received from the drug dispensing center. Investigational product will not be disposed until accountability has been fully monitored.

Medication containers must be returned at each visit, as compliance will be assessed by tablet counts. Noncompliance is defined as taking less than <80% or more than 120% of study drug during any outpatient evaluation period (visit to visit). Discontinuation for noncompliance is at the Investigator's discretion and is to be noted on the eCRF.

Compliance until Day 7 visit, Compliance between Day 7 and Day 14 visit and Overall Treatment Compliance will be present in continuous summary (Number, Mean (SD), Median and Min, Max)

Categorized Overall Compliance [n (%)]

- < 80%
- 80% - 120%
- >120%

#### 6.2.5. Days of Study Termination

Days of study termination = End of study date – Randomization date + 1.

#### 6.2.6. Study Completion

A subject will be defined as "completed" if she/he remained in the study up to End of study (see End of study CRF). Termination at a time point and prior to this will be considered as discontinuation.

#### 6.2.7. Duration of AE

Duration of AE [days] = Date of stop of AE – Date of start of AE + 1.

#### 6.2.8. Prior/Concomitant Medication

A medication is regarded as 'prior' if the stop date of the event is prior to the first dose of study drug, irrespective of the start date.

A medication is regarded as 'concomitant' if it is not 'prior' and the start date or stop date is between the date of first dose of study drug (included) and the End of study date (included).

A medication is regarded as 'concomitant' if ticked as ongoing on the CRF.

#### 6.2.9. Study Day 1

Study day 1 will be the first day of study drug administration.

First day of study drug administration is defined as first dispensation date + 1.

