### **7.1.2 Dosing Period**

[figure not shown]
Once these washout periods have been completed, patients will attend the clinic for randomization and baseline (Day 0) assessments; patients will provide a blood sample for PK analysis. After completion of baseline (Day 0) assessments, study drug will be dispensed to patients and they will take their first dose the next day (Day 1); patients will receive enough study drug to last until the next visit at Day 7. On Day 7 ( $\pm 1$  day), patients will attend the clinic for an outpatient visit, when efficacy and safety assessments will be undertaken. Patients will provide a blood sample for PK analysis at the estimated trough (just prior to dosing) and at the estimated maximum plasma concentration of SUVN-G3031 ( $3 \pm 0.5$  hours postdosing). Patients will be dispensed enough study drug to last until the next visit at Day 14. On Day 14 ( $\pm 1$  day), patients will attend the clinic for an outpatient visit, where efficacy and safety assessments will be undertaken. They will provide a sample for PK analysis as per the Day 7 visit.

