### 9.2 Dosage Schedule

Patients should take 1 tablet per day in the morning, as soon as they wake up, with approximately 250 mL water. Dosing may occur with or without food. Patients will be dosed for 14 days.

If a patient forgets to take their morning dose and remembers before 1:00 PM, then they should take it as soon as they remember. If a patient forgets to take their morning dose and remembers after 1:00 PM, then they should skip the day's dose and take the next scheduled dose the next morning. If the patient has missed more than 1 dose, then they should only take the most recent forgotten dose.

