## 11.7 Sleep Diary

The sleep diary uses the following headers in a table that patients should complete daily, in relation to the onset, duration, and quality of sleep:

The form consists of 14 rows, each starting with a small black square (representing a column for a checkbox or similar input) followed by a longer black rectangle (representing the main header text area). The rows are vertically aligned and extend from the top of the page down to the bottom of the redacted area.

The diary will be completed electronically using a handheld eDiary.

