- m Sleep diary is collected nightly by the subject from Screening through Visit 3. The subject will provide the sleep diary from the preceding week at the beginning of each visit. In addition, dosing data will be collected in the diary.
- n Washout period will occur within a maximum 28-day Screening period to allow for minimum drug free period of  $\geq 7$  days for all stimulants targeting EDS, and  $\geq 14$  days for all agents targeting cataplexy prior to randomization and baseline (Day 0) assessments.
- o At the start of each visit as indicated, the subject will return IP that has not been used, provide sleep diary, report any modification in concomitant medication dosage or regimen, and research personnel will complete a nondirected inquiry for the detection of AEs. Safety assessments completed by the Investigator precede the efficacy assessments.
- p Concomitant medications and AEs may be collected prior to the PSG and the first MWT.

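### SAP 6.2.9 fixes the first dose date as dispensing date + 1 for every subject, so off-schedule starters get a wrong treatment start and possibly wrong TEAE and AESI flags

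*SAP*

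**What the plan says.** SAP 6.2.9 contains two statements. The first is that "Study day 1 will be the first day of study drug administration". The second is that "First day of study drug administration is defined as first dispensation date + 1". No visible text restricts the second statement to missing data or gives precedence to a recorded dose date.

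Both documents plan for dosing to be recorded. The diary footnote to the schedule of assessments (footnote m of Table 1 in the protocol and in the SAP) says "In addition, dosing data will be collected in the diary". Protocol 11.7 adds that "The diary will be completed electronically using a handheld eDiary". SAP 6.2.4 refers to diary dosing entries when it settles who was treated: "Subjects with missing sleep diaries or with missing entries in sleep diaries for dosing will be considered as treated", on condition that fewer tablets come back than were dispensed.

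The planned sequence (Protocol 7.1.2, SAP 3.4) is dispensing on Day 0 and a first dose at home on Day 1. Protocol 9.2 covers a forgotten morning dose. Patients who remember only after 1:00 PM are told that "then they should skip the day's dose and take the next scheduled dose the next morning".

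Several SAP definitions depend on when dosing began: the TEAE definition and classification table and the AESI restriction in 10.3, prior/concomitant status in 6.2.8, and the baseline in 6.2.1, where "the last non-missing valid observation before first dose of study drug will serve as the baseline measurement".

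**The concern.** The SAP uses the diary to help decide whether a subject was treated but ignores it when deciding when treatment began. A planned date replaces an observed one for everyone, including subjects whose diary shows something else.

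The first dose is taken unsupervised, the day after the clinic visit. A subject who forgets it and remembers after 1:00 PM starts on Day 2 while following the dosing instructions, so a late start does not require a protocol departure.

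What is at stake is safety attribution. Safety and tolerability are in the study title, and the TEAE tables depend on this date. Both AESIs concern sleep (vivid or unpleasant dreams; difficulty initiating or maintaining sleep) and count only after treatment has started, so one misassigned night can change an AESI flag. Protocol 5.2.2 reports dyssomnia (33.3%) and abnormal dreams (27.8%) as the most frequent TEAEs in Phase 1.

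**Working it through.** The plan states no figure to reproduce. The check is day arithmetic, followed by tracing which outputs use the date.

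**Inputs.** Dispensing is on Day 0 and the planned first dose on Day 1 (Protocol 7.1.2). The SAP date is 0 + 1 = Day 1 for everyone (SAP 6.2.9). An event is treatment-emergent if its start date is on or after the treatment start date (SAP 10.3). I assume that the treatment start date in that table is the 6.2.9 date, since no other definition is visible. The actual start days below are scenarios, not data.

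**Step 1: error by actual start.** Error = SAP date minus actual date. Days to Day 14 = 14 − start day + 1. The last column matters only if exposure is counted this way, and SAP 10.1 gives no formula.

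| Actual first dose | Error (days) | Onset days misflagged | Days to Day 14: SAP vs actual |
|---|---|---|---|
| Day 0 | 1 − 0 = +1 | Day 0 after the dose, flagged not treatment-emergent | 14 vs 15 |
| Day 1 | 1 − 1 = 0 | none | 14 vs 14 |
| Day 2 | 1 − 2 = −1 | Day 1, flagged treatment-emergent | 14 vs 13 |
| Day 3 | 1 − 3 = −2 | Days 1 and 2, flagged treatment-emergent | 14 vs 12 |

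**Step 2: which outputs inherit the error.**
- TEAE and AESI flags: yes, through SAP 10.3.
- Prior/concomitant status: yes if the 6.2.8 text is programmed. The classification table in SAP 7.4 compares dates with the baseline visit and does not use this date.
- Exposure: only if it is counted from this date.
- Compliance (SAP 6.2.4, 10.2): no, it rests on tablet counts. Days to study termination (SAP 6.2.5): no, they run from randomization.
- Baseline: no. Protocol 10.2.1 puts all Visit 1 assessments, including the fourth MWT session, before dispensing, and the next scheduled visit is Day 7 (±1 day).
- Efficacy: no. The analyses use the Day 7 and Day 14 visits, and SAP 6.4 applies no visit windows.

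**Step 3: would the compliance data reveal a late start?** With 7 doses planned for Days 1 to 7, a Day 2 start with no other missed dose gives 6/7 = 86%, above the 80% limit. A Day 3 start gives 5/7 = 71%, below it. The Day 2 case, the one most easily reached under Protocol 9.2, would not be classed as noncompliant for that interval.

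**Step 4: is the first recorded dose a safe replacement on its own?** No. Suppose a subject doses from Day 1 but has no diary entries for Days 1 and 2. The first recorded dose is then Day 3, which is 3 − 1 = 2 days too late, and true TEAEs on Days 1 and 2 would be lost. For that subject dispensing date + 1 is correct. SAP 6.2.4 anticipates missing entries, so the replacement rule has to cover them.

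**The case against.** The strongest defence is that the rule reproduces the protocol schedule. It is exact for every subject who starts as planned, it applies identically in all arms, and it needs no diary data, which the SAP itself expects to be incomplete in places. The diary field list is redacted, so the documents show that dosing data are collected but not that a usable dose date exists. A late start over-counts TEAEs, which errs on the cautious side for safety. A Day 0 start is unlikely: dispensing follows the fourth MWT session, about 2 + 2 + 2 + 2 = 8 hours after awakening, while dosing is meant to be on waking. A Day 3 start would already show up as noncompliance.

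Much of this stands, and it limits the point. It does not justify keeping the assumed date where complete diary entries show another one. The Day 2 case stays within the dosing instructions and is not caught by the compliance limit. Being visible in compliance data would not correct a TEAE flag in any case.

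Some stronger readings are tempting but not supported:
- **Contaminated baseline.** SAP 6.2.1 refers to the first dose, but the order of procedures makes the scheduled baseline pre-dose whichever day dosing begins.
- **Exposure overstated by 1/14 = 7% per day.** This needs an exposure formula that the SAP does not give.
- **A count of affected subjects.** Assuming 3% to 10% off-schedule starts would give 171 × 0.03 ≈ 5 to 171 × 0.10 ≈ 17, but no rate has a source in the documents. It would also count subjects rather than misflagged events, which require an onset in the one- or two-day gap.

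**Conclusion.** The point holds, with a narrow reach. SAP 6.2.9 assigns an assumed treatment start to every subject, and the date is wrong for anyone who does not start on Day 1: one day too early for a Day 2 start, two for a Day 3 start, one too late for a Day 0 start. The consequence is misflagged TEAEs and AESIs with onset in that gap. There are possible knock-on errors in prior/concomitant status (under the 6.2.8 text) and in exposure days (if counted from this date). Baseline values and the ESS, CGI-S and MWT results are not affected. The number of subjects or events involved cannot be estimated from the documents.

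The conclusion rests on two assumptions: that the 10.3 table uses the 6.2.9 date as treatment start, and that the diary dosing data include a date. A reader might infer that the true date is certainly in the database and is being discarded. The redacted field list does not allow that to be said.

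**What to change.** Replace the second sentence of SAP 6.2.9 with a two-step rule:

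1. The first dose date is the first dose recorded in the diary, provided that the diary dosing entries from dispensing up to that date are complete.
2. If those entries are missing or incomplete and the tablet count shows dosing, the first dose date is the first dispensation date + 1. Flag these subjects in the exposure listing.

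The completeness condition prevents a gap in the diary from pushing the start date too late and removing true TEAEs.

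Before finalizing this, the sponsor should confirm that the diary captures a dose date. At the same time, state in SAP 10.3 that treatment start date means this date, give the exposure formula in 10.1, and reconcile the 7.4 table (baseline visit) with the 6.2.8 and 7.4 text (first dose).

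The core change costs one short SAP edit, one derivation and one listing flag. It needs no new data if the dose date is captured.

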### 6.3. Missing Data

### 6.3.1. Missing Dates

No missing date will be imputed.

### 6.3.2. Missing values

**Efficacy - Missing Values at Baseline:** If a value is missing at baseline but there are non-missing post-baseline values, the missing baseline will be imputed as the first post-baseline non-missing assessment of the subject.

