### **5.2.2 Clinical Studies**

The SUVN-G3031 Phase 1 program included 72 healthy volunteers and provided preliminary clinical safety and pharmacokinetic (PK) data. SUVN-G3031 was well tolerated in both single-dose (up to 20 mg oral [PO]) and multiple-dose administrations (up to 6 mg PO for 14 days). There were no deaths, serious adverse events (SAEs), or treatment-emergent adverse events (TEAEs) leading to discontinuation from the Phase 1 program. The most frequently reported TEAE preferred terms were dyssomnia (33.3%) followed by abnormal dreams (27.8%), and TEAEs that occurred most frequently were in the System Organ Class, Psychiatric Disorders.

A maximum tolerated single dose (20 mg PO) and maximally well tolerated multiple doses of 6 mg/day PO for 14 days were established using a sequential dose-escalation paradigm. Specifically, no significant changes in safety parameters including laboratory results, physical examinations, vital signs, fluid balance, suicidal ideation, and electrocardiogram (ECG) parameters were noted. Pharmacokinetic data suggest dose proportionality across a range from 0.1 mg to 20 mg after single administration of SUVN-G3031 PO, with the main terminal half-life of approximately 23 to 34 hours across dosages evaluated. Multiple oral administration exhibited dose-proportional increases in exposures across 1 mg to 6 mg dose range with steady state achieved in approximately 5 days. Approximately 55% to 60% of the administered dose was excreted via the urinary route. Food, gender, and age had no appreciable effect on the PK profile of SUVN-G3031.

SUVN-G3031 may be used adjunctively with a variety of compounds affecting EDS or cataplexy in patients with narcolepsy as outlined in the Investigator's Brochure. However, SUVN-G3031 is being evaluated as a monotherapy in the current protocol and all adjunctively used compounds affecting EDS or cataplexy in patients with narcolepsy are prohibited.

Further information on clinical studies can be found in the Investigator's Brochure.

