### 8.1 Inclusion Criteria

Individuals must meet all of the following criteria to be included in the study:

1. Must be between the ages of 18 to 65 years, inclusive.
2. Have narcolepsy with or without cataplexy (Na-1 or Na-2) based on the International Classification of Sleep Disorders (3rd Edition) criteria for the diagnosis of narcolepsy (new or previously diagnosed).
3. Have undergone an MSLT study showing an MSLT of  $\leq$  8 minutes with 2 or more SOREMPs performed according to standard techniques, with substitution of 1 of the required SOREMPs on MSLT with 1 obtained from the preceding nocturnal PSG, performed at the time of diagnosis. No other potential cause for EDS must have been identified during the preceding nocturnal PSG. If the study site is unable to obtain the MSLT diagnoses, the MSLT may be performed to confirm diagnoses upon Sponsor and medical monitor approval.
4. An ESS score of  $\geq$  12; and mean MWT time of  $<$  12 minutes across the first 4 sessions at baseline. An ESS score of  $\geq$  12 for eligibility is only required at the Baseline visit. An ESS score of  $<$  12 at Screening due to concomitant medications will be subjected to PI's discretion for eligibility.
5. Must have a body mass index ranging from 18 to  $<$  45 kg/m^2.
6. Negative urine drug screen (UDS) at the Screening and Baseline (Visit 1) visits.
  - A positive UDS at Screening can be repeated up to Day -1; however, a negative UDS is required prior to Day 0 (Baseline visit), and a second negative UDS is required on Day 0 (Baseline visit).
  - A positive UDS at Screening due to concomitant medications will be subject to PI's discretion for eligibility.
7. All patients must agree to remain free of alcohol and illicit drugs from Screening and until the Safety Follow-up visit.
8. All male patients who are sexually active and not surgically sterilized must agree to use a condom with or without spermicide, in addition to any birth control used by their partner during the study until 1 month after the final dose of investigational product (IP).
9. Before randomization, a woman must be either not of childbearing potential or of childbearing potential practicing highly effective methods of birth control.

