#### **14.3.2 Analysis of Secondary Efficacy Endpoints**

The secondary efficacy endpoints for this study are:

- Change from baseline in the mean CGI-S score related to EDS at Day 14
- Change from baseline in the mean MWT score at Day 14

To control the Type I error rate, the testing of secondary endpoints will be controlled using hierarchical testing methods. Thus, only if the primary endpoint is statistically significant, will the first listed secondary endpoint be tested. Likewise, the second listed secondary endpoint will only be tested if the first secondary endpoint is also statistically significant.

The secondary endpoints will be analyzed analogous to the analysis of the primary efficacy endpoint, i.e., an MMRM using the ITT population with the same factors, except the baseline value for the respective variable will be used instead of baseline total ESS score.

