## 8.1. Primary Efficacy Endpoint and Analysis (Primary Estimand)

The null ( $H_0$ ) and alternative ( $H_1$ ) hypotheses of the study are as follows:

H0: SUVN-G3031 and placebo do not differ in their change from baseline in the mean total ESS score at Day 14.

H1: SUVN-G3031 and placebo differ in their change from baseline in the mean total ESS score at Day 14.

[figure not shown]
The primary estimand is defined with the following 5 attributes:

The primary analysis approach will be performed using a mixed model repeated measures (MMRM) analysis. This model considers all observed post-baseline assessments of both post-baseline visits (Day 7 and Day 14), in case of death, the visits after the death will be filled with the worst observed value post-baseline, prior to entering the MMRM. In the MMRM all missing values will be imputed via direct likelihood based on the assumption of missing at random.

The MMRM model will include randomized treatment (for the pooled analysis, both active treatments will be combined), visit and treatment (for the pooled analysis, both active treatments will be combined) by visit interaction as explanatory variables, stratification factor for cataplexy subject history (presence or absence) and baseline MWT score as continuous covariates. An unstructured covariance structure will be assumed. Least square mean changes will be estimated for each single treatment and the difference of each SUVN-G3031 dose versus placebo. Results of comparison of pooled active treatment groups versus placebo will be presented. Additionally, the analysis will be repeated with consideration of single treatment groups.

If the assumptions underpinning the MMRM are found to be violated, either a log transform or an analysis based on ranked data will be performed as appropriate and least squares means, 95% confidence intervals, and p-values of the treatment comparisons (across visits and within visits) for descriptive purposes along with basic arithmetic summary statistics (mean, median, SD, standard error of the mean, min, and max) will be provided.

If the statistical comparison of pooled active dose group versus placebo results in superiority with p-values less or equal to 5% then SUVN-G3031 can be considered as superior to placebo in a confirmatory way. Otherwise result will be interpreted in an exploratory way.

---

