#### 8.4. Secondary Efficacy Endpoint(s) and Analyses (Secondary Estimands)

The secondary efficacy endpoints for this study are:

- Change from baseline in the mean CGI-S score related to EDS at Day 14
- Change from baseline in the mean MWT score at Day 14

The two secondary estimands investigate the efficacy endpoints 'Difference to placebo in the change from baseline in the CGI-S score related to EDS at Day 14' on the ITT population using a MMRM analysis, and the 'Difference to placebo in the Change from baseline in the MWT score at Day 14' on the ITT population using a MMRM analysis. MMRM considers all observed post-baseline assessments of both post-baseline visits (Day 7 and Day 14), , in case of death, the visits after the death will be filled with the worst observed value post-baseline from all subjects, prior to entering the MMRM In the MMRM all missing values will be imputed via direct likelihood based on the assumption of missing at random.

The approaches to handle intercurrent events for secondary endpoints will be consistent with those for the primary endpoint.

The testing of secondary endpoints will be controlled using hierarchical testing methods. The testing of the first secondary efficacy endpoint will be performed in a confirmatory way only, if for the primary efficacy of pooled treatment is significant versus placebo. The confirmatory testing approach will proceed to the second secondary efficacy endpoint only, if pooled active treatment comparison versus placebo is significant for the first secondary efficacy endpoint. Otherwise the results will be considered as exploratory only.

The secondary endpoints will be analyzed similar to the primary efficacy endpoint: using MMRM with multiple imputation and an ANCOVA of Day 7 and Day 14 data with multiple imputation as sensitivity analyses, and by repeating the analyses on PP as supportive analyses.

The time course (Baseline, Day 7, Day 14) of mean values of CGI-S and MWT, respectively, together with +/- standard error of mean will be presented in figures for the ITT and PP populations.

Summary tables by visit by treatment with actual and changes from baseline (if applicable) will be provided for the ITT and PP population.

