## **8.5. Analysis of Exploratory Endpoints**

Summary tables with actual and changes from baseline (if applicable) will be provided for the continuous exploratory endpoints (listed below), and they will be analyzed in a similar fashion as the primary endpoint, i.e., an MMRM using the ITT population and PP population. No imputations will be applied in the analysis of exploratory endpoints except total ESS score at Day 7, CGI-S score at Day 7 and MWT score at Day 7.

- Change from baseline in the mean total ESS score at Day 7
- Change from baseline in the mean CGI-S score related to EDS at Day 7
- Change from baseline in the mean MWT score at Day 7
- Change from baseline in the behavior of Sleep Diary parameters at Day 7 and Day 14 (7-day average)
- Changes in the behavior of the nocturnal overnight PSG assessments at Day 7 and Day 14
- Change in MWT score, within each of the 4 MWT sessions within a single day (Day 7 and Day 14)

Frequency tables will be provided. For binary assessments (listed below), a repeated measures responder analyses will use a generalized estimating equations with a logit link function and starting with an unstructured working correlation matrix. No imputations will be applied in the analysis of below endpoints.

- The proportion of subjects reporting CGI-C scores of 1 or 2 at Day 7 and Day 14 (EDS)
- Proportion of subjects reporting CGI-C scores of 1 or 2 or 3 at Day 7 and Day 14 (EDS)
- The proportion of subjects reporting CGI-S scores related to EDS of 1 or 2 at Day 7 and Day 14
- Proportion of subjects reporting CGI-S scores related to EDS of 1 or 2 or 3 at Day 7 and Day 14
- Proportion of subjects with improvement in the PGI-C score from baseline to Day 7 and Day 14
- Analysis of all endpoints (except Sleep Diary parameters and nocturnal overnight PSG assessments) evaluating SUVN-G3031 2 mg or 4 mg compared with placebo.

Factors included in the model will be treatment group, a stratification factor for cataplexy subject history, visit, treatment-by-visit interaction, and baseline value as a covariate. Model estimates will be based on Wald statistics.

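### SAP 6.3.2 fills a missing efficacy baseline with the first on-treatment value, so that visit's change is zero by construction; the practical exposure is CGI-S, the first gated secondary

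*SAP*

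**What the plan says.** SAP 6.3.2 covers efficacy values missing at baseline when later values exist: "the missing baseline will be imputed as the first post-baseline non-missing assessment of the subject". SAP 6.2.3 defines "Change = Post-baseline value – Value at baseline". SAP 6.2.1 takes baseline as the last valid value before first dose, but its opening words leave room for exceptions.

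The secondary endpoints are CGI-S and then MWT, both as change at Day 14. SAP 8.4 makes the sequence conditional on the pooled primary comparison: "The testing of the first secondary efficacy endpoint will be performed in a confirmatory way only" if that comparison is significant, and MWT follows only if CGI-S succeeds. Protocol 14.3.2 gives the secondaries the primary model, "except the baseline value for the respective variable will be used instead of baseline total ESS score". SAP 8.4 says only that they are analyzed similarly to the primary, and SAP 8.1 lists "baseline MWT score as continuous covariates". SAP 8.5 rules out imputation for the continuous exploratory endpoints "except total ESS score at Day 7, CGI-S score at Day 7 and MWT score at Day 7".

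**The concern.** A baseline should describe the patient before treatment. This rule replaces it with a value that treatment may already have changed, and then subtracts that value from later ones. For an affected patient, whatever was gained or lost by the donor visit disappears from the endpoint. If the model adjusts for the endpoint's own baseline, the same treatment-affected value also becomes the covariate.

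The exposure differs by endpoint:

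- **ESS.** Protocol 8.1 requires a qualifying score at Baseline ("12 for eligibility is only required at the Baseline visit"). There is also a Screening value to fall back on, and SAP 5.2 makes a baseline primary assessment a condition of ITT.
- **MWT.** The baseline mean over four sessions is an eligibility measure.
- **CGI-S.** The schedule has a single pre-dose rating, at Visit 1. It is not an eligibility criterion and ITT does not require it.

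The weak spot is therefore the first confirmatory secondary. A loss there also closes the gate to MWT. If the imputation allowed by SAP 8.5 includes the baseline fill, constructed zeros also enter the Day 7 CGI-S analysis, since Day 7 is the usual donor visit.

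**Working it through.** **Inputs.** From the documents: the fill rule and change definition above, 1:1:1 allocation (2:1 pooled active to placebo), a maximum of 171 randomized and 10% dropout (SAP 3.6). The plan gives no figure for missing baselines. Its sample size of 38 per group does reproduce (34 per arm by a t-based calculation, 34/0.9 = 37.8), but nothing here depends on it. Assumed, because the documents are silent:

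- missing-baseline fraction f of 1, 2, 5 or 10%
- equal visit correlations r of 0.3 to 0.7
- a true pooled effect of −0.60 SD at Day 14
- all or half of that effect present by Day 7

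Protocol 5.2.2 reports "steady state achieved in approximately 5 days", which makes an early full effect plausible but does not show it.

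**One patient.** True CGI-S is 5 at baseline, 4 at Day 7 and 3 at Day 14.

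| | Baseline used | Day 7 change | Day 14 change |
|---|---|---|---|
| True | 5 | −1 | −2 |
| Rule, Day 7 observed | 4 | 0 | −1 |
| Rule, Day 7 missing | 3 | – | 0 |

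**Group level.** Let Δ7 and Δ14 be the true differences from placebo, with f equal across arms and Day 7 as donor.

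- Not adjusted for own baseline: the estimate is Δ14 − f·Δ7. With Δ7 = Δ14 the loss is the fraction f itself.
- Adjusted for own baseline: the constructed baselines differ between arms by f·Δ7. The slope of the Day 14 value on baseline is about r, so the estimate is about Δ14 − r·f·Δ7 and the relative loss is r·f·Δ7/Δ14.

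**Simulation of the adjusted analysis** (1.5 million patients per cell, 2:1 allocation, ANCOVA of Day 14 change as a large-sample stand-in for the MMRM), for r from 0.3 to 0.7:

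| Missing | Loss, full effect by Day 7 | Loss, half by Day 7 |
|---|---|---|
| 1% | 0.3-0.7% | 0.2-0.4% |
| 2% | 0.6-1.4% | 0.3-0.7% |
| 5% | 1.5-3.5% | 0.7-1.8% |
| 10% | 2.9-6.9% | 1.5-3.4% |

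The formula agrees. At r = 0.5 and f = 5% the shift is 0.5 × 0.05 × 0.60 = 0.015, and the simulation moved from −0.601 to −0.586. At 10% the shift is 0.030, and it moved from −0.601 to −0.571.

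**Trial-size check.** This used 102 active and 51 placebo, SD 1.0, a true effect of −0.50 at both visits, r = 0.5 and 3,000 runs. The adjusted estimate went from −0.498 with none missing to −0.482 at 5% and −0.473 at 10%. Power went from 0.910 to 0.901 and 0.875.

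**Patients.** 171 × 0.9 = 153.9, about 154. Rates of 1, 5 and 10% are about 2, 8 and 15 patients.

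**Null.** With Δ7 = Δ14 = 0 and equal f, both expressions give 0. Simulated estimates agreed with the no-missing case within 0.001 SD. Trial-size type I error was 0.044 to 0.054.

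**Unequal missingness** (placebo also improving by 0.4 SD at Day 7, full effect by Day 7). The adjusted shift is about r times [active f × (−1.0) − placebo f × (−0.4)].

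- 10% active, 2% placebo: −0.100 + 0.008 = −0.092. Simulated attenuation is 4-10%.
- 2% active, 10% placebo: −0.020 + 0.040 = +0.020. Simulated inflation is 1-2%.

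**Variability.** The rule does not understate it. At r = 0.5 the Day 14 residual SD goes from 0.865 to 0.867 at 5% missing and from 0.866 to 0.869 at 10%.

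**The case against.** The strongest reply is that the trigger is rare and the error conservative. Baseline CGI-S is rated on site in a fixed order on the day of randomization (Protocol 10.2.1), so a missing value is a procedural slip. Nothing in the documents supports 5 or 10%, and at 1-2% missing the loss is 0.2-1.4%. The constructed zero usually falls on Day 7, which is exploratory; Day 14 CGI-S is zero only if Day 7 is missing too. Type I error is not inflated, and the power gained by changing the rule is negligible at low rates. Because CGI-S is rated before randomization, imbalance between arms should arise mainly by chance, so the unequal cases are illustrations and not an expected bias. All of this stands, and it limits the size of the problem.

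A second reply is that the SAP overrides the protocol where they differ (Protocol 14). If SAP 8.1's baseline MWT carries over to CGI-S, the contaminated covariate disappears. That is a fair reading, but it makes the attenuation larger: the loss is then about the missing fraction itself when the full effect is present by Day 7.

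Third, SAP sections 8.2 and 8.3 and the appendix are not visible and may contain sensitivity analyses. Those could qualify the result, but they would not make the stated rule sound.

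**Conclusion.** The concern holds; the rule is wrong as written. The zero at the donor visit and the loss of the first week's effect from the Day 14 change follow directly from SAP 6.2.3 and 6.3.2, with no assumptions. The size does rest on assumptions. With the full effect by Day 7, r of 0.3 to 0.7, equal missingness and adjustment for own baseline, the loss is under 1.5% at up to 2% missing and 2.9-6.9% at 10%. Half the effect by Day 7 roughly halves this. The direction is toward no effect, and there is no bias under the null when missingness is equal.

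This should be corrected, but it does not threaten the primary analysis. The reason to act is that a confirmatory endpoint, and the gate to MWT, should measure change from the pre-treatment state. The SAP also leaves unsettled whether 6.3.2 is an exception to 6.2.1 and whether 5.2 keeps the rule away from ESS.

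**What to change.** Delete the rule in SAP 6.3.2 and state three things:

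1. SAP 6.2.1 has no exception: baseline is a pre-dose value only.
2. SAP 5.2 governs ESS: a subject with no pre-dose ESS is not in ITT.
3. For CGI-S and MWT, one named method replaces the rule. Either use a constrained longitudinal model, with baseline in the response vector and a common baseline mean across arms, or fill with the all-arm mean of observed pre-dose baselines within cataplexy stratum, using neither treatment arm nor post-baseline data. The mean fill is the smaller change because it keeps the planned MMRM.

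Say also which own-baseline covariate the CGI-S and MWT models use, state whether the SAP 8.5 imputation covers baseline, and report missing baselines by arm.

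The cost is SAP wording and a few program lines, and affected CGI-S and MWT patients stay in the analysis. In simulation the mean fill was within 0.1% of the no-missing estimate in every equal-missingness cell. Against having no missing baselines, its SE rises by 0.3-2.4% at 5% missing and 0.5-4.7% at 10%. The benefit is a correctly defined estimate; little power is gained.
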